## 6 RATIONALE AND BACKGROUND

### 6.1 VON WILLEBRAND DISEASE

Inherited von Willebrand disease (VWD) is the most common inherited haemorrhagic disorder, with an estimated prevalence of 1 in every 1000 individuals of either sex. There is wide geno- and phenotypic variability of the disease, and not all patients with VWD require treatment.

Three types of inherited VWD are known. Whereas type 1 and type 3 disease are characterised by a quantitative deficiency of von Willebrand factor (VWF), VWD type 2 arises from a qualitative deficiency of VWF. There are various subtypes within the three inherited types of VWD. VWD may also be acquired.

Of the inherited forms, type 1 is the most common, accounting for 70–80% of cases, followed by type 2, which affects approximately 20% of patients. Type 3, the most severe form of VWD characterised by a complete absence of VWF, is rare and affects about 1–3% of all patients [1].

Treatment of VWD depends on the type and severity of the disease. Whereas mild to moderate forms of type 1 and type 2A disease often respond adequately to treatment with desmopressin (1-deamino-8-D-arginine vasopressin, DDAVP), DDAVP is contraindicated in type 2B and not effective in type 3 disease. Treatment with DDAVP may also be contraindicated for other clinical reasons or may be associated with significant side effects.

The appropriate treatment for the patients in whom DDAVP is ineffective or contraindicated are VWF/factor VIII (FVIII) concentrates, which have become the mainstay of VWD treatment. Cryoprecipitate, which is screened for viruses but not treated to inactivate them, is also rich in VWF, but is likely to be less safe than the viral-attenuated concentrates [2].

VWD affects all ethnic groups and both sexes. Women are more likely to experience symptoms of VWD and may pose a special treatment challenge because of the physiological events related to menstruation, pregnancy, and birth [3]. If untreated, pregnant women with VWD are at increased risk of postpartum bleeding. In women with VWD types 1 or 2, the levels of VWF and FVIII rise 2- to 3-fold during the second and third trimesters, but fall to baseline levels soon after delivery. By contrast, in VWD type 2B, the increase of the abnormal VWF can cause or worsen thrombocytopenia. In women with VWD type 3, VWF and FVIII do not increase during pregnancy, so that administration of VWF-containing products may be required during pregnancy and at birth [3].

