### 8.3.2 Inclusion Criteria

Patients who meet all of the following criteria are eligible for the study:

1. Male or female patients aged  $\geq 5.5$  years at the time of enrolment
2. VWD type 1 (baseline von Willebrand factor activity [VWF:RCo],  $< 30$  IU/dL), 2A, 2B, 2M, or 3 according to medical history requiring substitution therapy with a VWF-containing product to control bleeding
3. Currently receiving frequent on-demand treatment with a VWF-containing product
4. In female patients of child-bearing potential using hormonal contraception, the medication class should remain unchanged for the duration of their study participation
5. Voluntarily given, fully informed written and signed consent obtained before collection of any patient data

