3.2 Per Protocol Set

The **per-protocol (PP) set** is a subset of the FAS that will exclude subjects with important protocol deviations which may have an impact on the evaluation of the primary study outcome parameter.

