4.7.1 Primary Endpoint

Primary endpoint of this study is to estimate the total annualized bleeding rate (TABR) during on-demand treatment with any VCP.

TABR will be calculated as the total number of spontaneous bleeds, traumatic bleeds and other bleeds in the time period between screening visit and the study completion visit, divided by the duration (in years) between first dose of VCP and the study completion visit. Surgery periods, and BEs occurring within these surgery periods, will be excluded from the calculation of TABR. Menstrual bleeds will not be included in this calculation, but reported and analyzed separately.

Descriptive statistics for TABR along with exploratory 95% Confidence Intervals will be presented.

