4.7.4 Menstrual Bleedings (only female patients of childbearing potential)

For female patients, the results of the PBAC score over time will be summarized in descriptive tables for each complete menstrual cycle including changes to baseline.

Annualized rates of heavy menstrual bleedings will be calculated in analogy with TABR and summarized in descriptive tables. For the exploratory endpoint 'Annualized rate of heavy menstrual bleeds' descriptive statistics will be tabulated.

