6 DERIVATIONS AND TRANSFORMATIONS

6.1 Formulas for derived variables

Variable	Description
Durations between two dates	Later date minus earlier date plus 1, expressed in days. (Remark: Duration will be 1, if both dates are the same.)
Surgery Period	(Date of surgery – date of last VCP treatment for surgery + 1)/365.25
Total Annualized Bleeding Rate (TABR)	Number of bleedings excluding menstrual bleedings / (date of study completion – date of screening + 1)/365.25 (Surgery periods, and BEs occurring within these surgery periods, will be excluded from the calculation of TABR. BEs occurring at day of surgery but prior to start of surgery/start of treatment for surgery will be included into calculation)
Spontaneous Annualized Bleeding Rate (SABR)	Number of spontaneous bleedings / (date of study completion – date of screening + 1)/365.25 (Surgery periods, and BEs occurring within these surgery periods, will be excluded from the calculation of SABR. BEs occurring at day of surgery but prior to start of surgery/start of treatment for surgery will be included into calculation)
Traumatic Annualized Bleeding Rate (TRABR)	Number of spontaneous bleedings / (date of study completion – date of screening + 1)/365.25 (Surgery periods, and BEs occurring within these surgery periods, will be excluded from the calculation of TRABR. BEs occurring at day of surgery but prior to start of surgery/start of treatment for surgery will be included into calculation)
Heavy Menstrual Bleeding Rate (HMBR)	Number of heavy menstrual bleedings* / (date of study completion – date of screening + 1)/365.25 (* for a definition refer to section 6.4)
ED	Exposure day = each calendar day the subject received VCP

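### The heavy menstrual bleeding rate keeps follow-up after conception and after hormonal contraception changes, and the per-protocol set does not reliably correct this

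*SAP*

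**What the plan says.** **Entry and conduct.** Protocol 8.3.3 excludes women who are pregnant or suspected to be so at enrolment, and women whose hormonal contraception changed in the preceding 6 months. During the study, Protocol 8.3.2 (criterion 4) asks: "In female patients of child-bearing potential using hormonal contraception, the medication class should remain unchanged for the duration of their study participation". The protocol has no rule for ending menstrual follow-up if contraception is started or changed later, or if a woman conceives.

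**Menstrual analyses.** SAP 4.7.4 says "Annualized rates of heavy menstrual bleedings will be calculated in analogy with TABR and summarized in descriptive tables", and SAP 6.1 gives the formula "Number of heavy menstrual bleedings* / (date of study completion – date of screening + 1)/365.25". For PBAC, SAP 4.7.4 says "the results of the PBAC score over time will be summarized in descriptive tables for each complete menstrual cycle including changes to baseline". PBAC is a listed secondary endpoint (Protocol 8.2.2, SAP 4.7.2). HMBR is not; SAP 4.7.4 says "For the exploratory endpoint 'Annualized rate of heavy menstrual bleeds' descriptive statistics will be tabulated".

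**Analysis sets.** The per-protocol (PP) set in SAP 3.2 removes patients with "important protocol deviations which may have an impact on the evaluation of the primary study outcome parameter". That parameter is TABR, and SAP 4.7.1 says of it: "Menstrual bleeds will not be included in this calculation, but reported and analyzed separately". SAP 2.3 is wider: it treats violations of important eligibility criteria as important because they may make results less reliable, and leaves their consequences to the data review meeting. SAP 4 and 4.7 drop the PP analysis of endpoints other than the primary when the two sets differ by 5% or less.

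**Other rules.** SAP 4.1.2 limits bleeding rates to documented time. SAP 4.8.2 puts pregnancies into individual listings only.

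**The concern.** The entry criteria treat pregnancy and contraceptive change as things that distort the bleeding picture, but the menstrual analyses do not carry this through. Once a woman is enrolled, her HMBR denominator keeps running whatever happens.

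The two situations differ. After conception she is no longer at risk of a menstrual bleed, so the added time can only dilute the rate. After a contraceptive start, stop or class change she is usually still at risk, but her menstrual loss may move for reasons unrelated to on-demand VWF treatment: down if menses are suppressed, up if contraception is stopped.

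Menstrual bleeding intensity is a stated secondary objective, and Protocol 6.2 intends the data for historical comparison with a prophylaxis study. A level lowered by contraception or pregnancy could be read there as the on-demand pattern.

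**Working it through.** **The plan's own figure.** The only design figure is the half-width of the 95% interval for the mean ABR (Protocol 8.8, SAP 1.4): 1.96 × 3/√55 = 0.793, which rounds to the stated 0.8. No figure is given for HMBR or PBAC, so the rest is illustration.

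**Inputs.**
- From the documents: follow-up of about 6 months (taken as 183 days), 55 patients, and the SAP 6.1 formula, read as events divided by (days/365.25).
- Assumed: 12 heavy menstrual bleeds per year before the event, the date of the event, the degree of suppression, and the share of women affected.

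**One woman, conception or full suppression at day 61.** About 12 × 61/365.25 = 2.0 bleeds occur before the event.
- Whole period: 2/(183/365.25) = 3.99 per year.
- Time ended at the event: 2/(61/365.25) = 11.98 per year.
- Ratio: 61/183 = 0.33, whatever the starting rate.

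**One woman, contraceptive change at day 91, partial effect.** Whole-period HMBR = 12 × [91 + (1 − r) × 92]/183, where r is the reduction in heavy bleeds after the change.

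| r | 0% | 25% | 50% | 75% | 100% |
|---|---|---|---|---|---|
| HMBR per year | 12.0 | 10.5 | 9.0 | 7.5 | 6.0 |

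**Cohort mean.** If a share p of women has full suppression from day c, the relative change is −p × (183 − c)/183.
- p = 5%, c = 122: −1.7%
- p = 10%, c = 91.5: −5.0%
- p = 20%, c = 61: −13.3%

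With 1 to 3 of an assumed 20 women fully suppressed from mid-study, the mean is 12 × (1 − 0.5 × 1/20) = 11.7 to 12 × (1 − 0.5 × 3/20) = 11.1, that is −2.5% to −7.5%.

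**Does another rule remove this time?**
- *Documented time only (SAP 4.1.2):* no. Time after conception or a contraceptive change is still documented.
- *Analogy with TABR (SAP 4.7.4):* no. TABR removes surgery periods only.
- *PBAC per complete cycle:* this keeps pregnancy time out, since there are no cycles to enter. Cycles after a contraceptive change stay in.
- *PP set:* not reliably. It is tied to an outcome without menses. Conception is not a named deviation, and criterion 4 is worded for women already using hormonal contraception, so a new start is not named either. Exclusion removes the whole patient. Outside the primary endpoint, PP analyses need a difference above 5%: 0.05 × 55 = 2.75, so at least 3 patients if 55 are enrolled.

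**The case against.** **What stands.** A reader might infer that the PP set can never remove affected women. The documents do not support that. A class change in a woman already using hormonal contraception breaches criterion 4, and SAP 2.3 lets the data review meeting exclude her. Pregnancy could also be judged relevant to TABR, since Protocol 6.1 says that in types 1 and 2 "the levels of VWF and FVIII rise 2- to 3-fold during the second and third trimesters". A reader might also infer that pregnancy time dilutes PBAC. It does not, because PBAC has no time denominator. A shift in PBAC after a contraceptive change would show in summaries over time, although the cause would not.

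The scale is modest. HMBR is exploratory and the study is descriptive. The menstrual objective is not pursued in Croatian centres. Entry criteria favour stable contraception, and the number of affected women is unknown. Medication dates and pregnancies are listed, so affected women could be traced.

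The strongest point concerns the remedy. All observed time is a legitimate basis for describing routine care, and women may start contraception because they bleed heavily. Stopping at that date would then select their worst period. Very short follow-up also gives unstable rates: one bleed by day 10 is 1/(10/365.25) = 36.5 per year.

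**What does not stand.** None of this justifies counting time after conception, when no menstrual bleed is possible. Listings do not correct a summary rate, and a case-by-case decision on whole patients is not a rule for affected time.

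**Conclusion.** The point holds for HMBR in respect of both pregnancy and contraceptive change, and for PBAC in respect of contraceptive change only. The PP set may catch some cases but is not a reliable correction.

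For an affected woman the effect can be large: about one third of her earlier rate after conception or full suppression at day 61. For the cohort it is about −2% to −13%, on assumed shares of 5% to 20% of women, full suppression, and events between day 122 and day 61. Partial suppression gives less. Stopping contraception would act in the opposite direction, by an amount that the documents give no basis to size.

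It would be wrong to infer that the primary result is compromised. TABR excludes menses. Any effect of pregnancy on it would come through the rise in factor levels, which Protocol 6.1 places in the second and third trimesters and does not describe for type 3. Follow-up is only about 6 months, and women known or suspected to be pregnant at enrolment are excluded. This is a worthwhile SAP correction to secondary and exploratory menstrual results, not a flaw in the main analysis.

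**What to change.** Before database lock, amend SAP 4.7.4 and 6.1 as follows.

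1. **Main HMBR analysis.** End both the event count and the follow-up time at the estimated start of pregnancy or at study completion, whichever comes first. Use the best available date and state its source. The Pregnancy Form, which asks for the last menstrual period, is required only for patients treated with Wilate (Protocol 10.1.2), and Table 3 records pregnancy status only at screening.
2. **Sensitivity analysis of HMBR and PBAC.** End menstrual follow-up at the first start, stop or class change of hormonal contraception, taken from the concomitant-medication dates (SAP 4.5). Report how many women are affected.
3. **Short follow-up.** In that analysis, also give HMBR as total events over total time. For example, take 19 women with 6 bleeds in 183 days and one woman with 1 bleed in 10 days. The mean of individual rates is (19 × 11.98 + 36.5)/20 = 13.2, against 115/(3,487/365.25) = 12.0 in total.

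A supportive TABR ending at the estimated start of pregnancy is optional.

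The cost is SAP wording, one derived cut-off date per event type and a few extra tables. Some menstrual follow-up is lost in affected women, and some pregnancy dates will be approximate. The contraceptive cut-off should remain a sensitivity analysis, because contraception started in response to heavy bleeding would make it selective.

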1.2 Secondary objective

The secondary objectives of this study are to:

- Assess the quality of life (QoL) of VWD patients undergoing on-demand treatment with a VCP
- Assess the safety of the VCP used for on-demand VWD treatment

The following objectives are also pursued except for Croatian centers:

- Determine the effectiveness of the VCP used in the treatment of bleeding episodes (BEs)
- Determine the effectiveness of the VCP used in surgical prophylaxis
- Assess the patients' joint status using the Hemophilia Joint Health Score (HJHS)
- Assess the menstrual bleeding intensity of female patients of child-bearing potential

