4.1 Conventions

4.1.1 Baseline definition

Assessments performed at or shortly before the screening visit are considered as baseline. If more than one measurement of the same item satisfies this condition, the most recent measurement is considered as baseline. Collection of PBAC assessment was not included in protocol version V01. For subjects starting with protocol version V01, the first assessment under protocol version V02 serves as baseline.

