4.1.3 Pooling of centers

All tables will be presented in total over all participating countries and centers. The distribution of number of subjects per country and center will be presented in the disposition section of the report.

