4.7.2 Secondary Endpoints

Secondary endpoints are:

- Spontaneous annualized bleeding rate (SABR), calculated in analogy with TABR
- Data on the consumption of VCP product (VWF/FVIII IU/kg per month per patient) used for routine on-demand treatment

The following secondary efficacy endpoints will be studied except in Croatian centers:

- Effectiveness of VCP in the treatment of BEs based on the proportion of successfully treated BEs (definition see section 6.2)
- Effectiveness of surgical prophylaxis with VCP based on the proportion of successfully treated surgeries (definition see section 6.3)
- Pictorial Blood Loss Assessment Chart (PBAC) score

Regarding the VCP administration data, the following parameters will be documented:

- Dates and times of VCP injections
- Doses of VCP in IU and IU/kg and VCP batch numbers
- Reason for VCP injection (prophylaxis, treatment of BE, surgery)

Statistical Analysis Plan	Version 3.0		Page 12 of 17
Sponsor	Octapharma	Protocol No	WIL-29

Descriptive statistics will also be presented for the SABR and for time in study, exposure days, number of infusions and dosages of VCP overall and by reason for VCP injection.

Additionally, descriptive statistics will be presented for the traumatic annualized bleeding rate (TRABR), calculated in analogy with TABR.

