6.4 Criteria for Heavy Menstrual Bleeding

Any menstrual bleeding that meets any of the following criteria will be classified as Heavy Menstrual Bleeding for analysis purposes:

- Interferes with daily activities such as work, housework, exercise, or social activities,
- Requires changing pads/tampons more frequently than hourly (referred to as 'flooding'),
- Lasts 7 or more days,
- Includes the presence of cloths > 1 cm combined with a history of flooding,
- PBAC score ≥ 185 , whenever PBAC score are applicable.

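### One pooled rate of heavy menstrual bleeding mixes time with and without the PBAC criterion, so it can be biased low

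*SAP*

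**What the plan says.** - **The rate.** SAP 6.1 gives HMBR as "Number of heavy menstrual bleedings* / (date of study completion – date of screening + 1)/365.25". The row has no limit by protocol version or centre. SAP 4.7.4 calls it an exploratory endpoint, to be calculated like the total annualised bleeding rate (TABR) and summarised descriptively.
- **The case definition.** SAP 6.4: "Any menstrual bleeding that meets any of the following criteria will be classified as Heavy Menstrual Bleeding for analysis purposes". Four criteria need no chart score: interference with daily life, changing protection more than once an hour, duration of at least seven days, and clots over 1 cm with a history of flooding. The fifth is "PBAC score ≥ 185 , whenever PBAC score are applicable".
- **PBAC by protocol version.** SAP 4.1.1: "Collection of PBAC assessment was not included in protocol version V01". It goes on: "For subjects starting with protocol version V01, the first assessment under protocol version V02 serves as baseline". So the SAP expects some women to have follow-up without PBAC.
- **PBAC by country.** SAP 1.2 introduces a list that includes menstrual bleeding intensity with "The following objectives are also pursued except for Croatian centers". SAP 4.7.2 introduces a list that includes the PBAC score with "The following secondary efficacy endpoints will be studied except in Croatian centers".
- **Pooling.** SAP 4.1.3: "All tables will be presented in total over all participating countries and centers". SAP 4.7.3, 6.2 and 6.3 each restate the Croatian exclusion. SAP 4.7.4, 6.1 and 6.4 do not.

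**The concern.** The numerator depends on which criteria could be applied, and the denominator does not. In V02 time outside Croatia a bleed can qualify in five ways. In V01 time, and in Croatian centres if their patients are included, it can qualify in at most four. A heavy bleed that only the PBAC score would reveal is counted in the first kind of time and cannot be counted in the second, yet both kinds enter one denominator.

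TABR leaves out menstrual bleeds, so HMBR is the only planned rate for heavy ones. Protocol 6.2 says the data will serve as a basis for historical comparison with a study of prophylactic treatment. A rate whose definition depends on when and where a woman enrolled is a weak basis for that. The SAP text names no analysis that would show the mixture.

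**Working it through.** **The plan's own figures.** The SAP states no expected value or precision for HMBR. Its only precision figure, ±0.8 for the mean ABR (SAP 1.4), reproduces as 1.96 × 3 / √55 = 0.793, but it does not bear on this point.

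**Inputs**
- λ: heavy menstrual bleeds per year under the full five-criterion definition.
- w: share of woman-time without PBAC. Not in the documents; assumed 0.1 to 0.5.
- q: share of heavy bleeds that meet the PBAC criterion and none of the other four. Not in the documents; assumed 0 to 0.5.

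HMBR is read as bleeds divided by years of follow-up. The bracketing of the printed formula is a separate matter. It is also assumed that λ is the same in both kinds of time and that the other four criteria were recorded throughout.

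**Formula.** Covered time, share (1 − w), yields λ. Uncovered time, share w, yields λ(1 − q). The pooled rate is

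λ(1 − w) + λw(1 − q) = λ(1 − wq),

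so the relative shortfall is w × q:

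| q | w = 0.10 | w = 0.25 | w = 0.50 |
|---|---|---|---|
| 0 | 0% | 0% | 0% |
| 0.10 | 1% | 2.5% | 5% |
| 0.25 | 2.5% | 6.25% | 12.5% |
| 0.50 | 5% | 12.5% | 25% |

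At the 25% corner, a rate of 8 per year is reported as 6. Under these assumptions the mechanism cannot push the rate up.

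**What drives w.** With 6 months of follow-up, a woman who starts under V01 and first has PBAC under V02 at month m has an uncovered share of m/6: 17%, 50% or 83% for m = 1, 3 or 5. A Croatian woman, if included, is uncovered throughout.

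**Checking possible remedies** (λ = 6 per year, q = 0.25, w = 0.5)
- As planned: 6 × (1 − 0.125) = 5.25 per year; a Poisson simulation also gave 5.25.
- Bleeds and time both limited to PBAC-covered time: 5.99 in simulation, so λ is recovered.
- Four criteria over all time: 6 × 0.75 = 4.5. This is a narrower quantity, but its definition is the same throughout.
- Denominator alone limited: (1 − wq)/(1 − w) = 0.875/0.5 = 1.75, or 10.5 per year. At q = 0.25 the ratio is 1.08, 1.25 and 1.75 for w = 0.10, 0.25 and 0.50. This overshoots and should not be done.

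**Where the covered window should start.** If it starts at the onset of a menstrual period, that period is always counted. Assuming 28-day cycles, a 91-day window then contains 4 menses (days 0, 28, 56, 84) against 91/28 = 3.25 expected, or +23%. A 30-day window contains 2 against 1.07, or +87%. A start at a visit date does not build in this excess.

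**The case against.** A reader might infer that the pooled rate is biased low as a matter of fact. The documents do not support that. The other four criteria are broad, and if every bleed scoring 185 or more also meets one of them, nothing is lost. What they support is that the rate can be low, by w × q.

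A reader might also infer that Croatian women are in the rate. That rests on silence in SAP 4.7.4 plus the pooling rule. SAP 1.2 points the other way, since it excepts the menstrual-intensity objective in those centres, and the missing restatement in 4.7.4 may be only a drafting gap. If they are out, only V01 time matters. This objection stands and limits the country part of the point.

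It can be said that the SAP already deals with the gap: SAP 6.4 applies the PBAC criterion only where a score is applicable, and SAP 4.1.2 bases bleeding rates on documented periods. The first lets the numerator definition vary and leaves time at risk untouched. The second does not mention PBAC coverage. Whether V01 time is documented for the other four criteria cannot be settled, because V01 is not among the documents. If those criteria were not recorded there, or in Croatian centres, w × q would be the wrong formula and the loss could be larger.

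A third inference is that a V01 starter's rate would appear to rise at the switch to V02. SAP 6.1 defines one rate per woman over her whole follow-up, so no output described in the SAP would show that. Only the PBAC score is summarised over time.

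Finally, HMBR is exploratory, is not among the listed secondary endpoints, and supports no confirmatory inference. That stands and lowers the priority.

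**Conclusion.** The inconsistency is in the current SAP text. One pooled rate combines time in which five criteria can apply with V01 time in which at most four can, and possibly with Croatian time as well. Confidence is high for that and low for its size. The shortfall is w × q: zero if no heavy bleed is detected by PBAC alone, and 1% to 25% for assumed values of 0.1 to 0.5 for each input. These figures rest on equal underlying rates in covered and uncovered time, and on the four other criteria having been recorded throughout. TABR and the other listed endpoints are not affected. The correction is worth making before analysis, because this is the only planned rate of heavy menstrual bleeding and it may be set beside another study's rate.

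**What to change.** In SAP 4.7.4 and 6.1:

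1. Report HMBR on the four non-PBAC criteria of SAP 6.4, over all follow-up in which those criteria were recorded, as the rate with one consistent definition.
2. Report the five-criterion HMBR with bleeds and time both limited to PBAC-covered time. Start the window at the visit date on which PBAC collection began under V02, not at the first menstrual period. Pool it as total bleeds over total woman-time, so that short windows do not dominate; with one month of coverage, a single bleed would count as about 12 per year in a per-patient rate.
3. State in SAP 4.7.4 that Croatian centres are excluded, consistent with SAP 1.2 and in the way 4.7.3 does it.

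The cost is SAP wording, one extra start-date variable and a little programming. The five-criterion rate will rest on less woman-time and so have a wider spread. It describes the whole follow-up only if bleeding was similar in covered and uncovered time.
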